
 • Adverse events (AEs) • Clinical laboratory tests • Physical examination (PE) • Vital signs • 12-lead ECGs • Epworth Sleepiness Scale (ESS) 	
 • Columbia Suicide Severity Rating Scale (C-SSRS) • Unified Huntington’s Disease Rating Scale (UHDRS) • Swallowing Disturbance Questionnaire (SDQ) • Unified Parkinson’s Disease Rating Scale (UPDRS) dysarthria item • Barnes Akathisia Rating Scale (BARS) • Hospital Anxiety and Depression Scale (HADS) • Montreal Cognitive Assessment (MoCA) 		

ENDPOINTS	
• Incidence of adverse events (AEs), serious AEs, severe AEs, drug related AEs, AEs leading to withdrawal during the following periods:
• Overall• During titration in Rollover subjects (up to 8 weeks)• During dose adjustment in Switch subjects (up to 4 weeks)• During long term treatment• Observed values and changes from baseline in clinical laboratory parameters (hematology, chemistry, and urinalysis)• Observed values and changes from baseline in vital signs• Observed values in ECG parameters and abnormal findings• Number of subjects with on-treatment QTcF values > 450ms, > 480ms, > 500ms• Observed values and changes in UHDRS, UPDRS (dysarthria), BARS, HADS, ESS, C-SSRS, and MoCA[®]• Duration of time to achieve stable dosing of SD-809 ER
------------------	---

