5.2.2 Dosing in Switch Subjects

For Switch subjects, the initial SD-809 ER dosing regimen will be based on the subject's incoming total daily dose of tetrabenazine. As outlined in Table 1 and Appendix 14, an initial dosing regimen of SD-809 ER will be assigned which targets a steady state AUC of total ($\alpha+\beta$)-HTBZ that is comparable to that of the subject's tetrabenazine regimen (Table 1).

After initial dose conversion, the investigator may adjust the dose of SD-809 ER upward or downward over the following 4 weeks, if necessary, to a level in which adequate chorea control has been achieved and the subject is tolerating the treatment regimen. Changes in dose should not be made more often than once per week unless the subject is experiencing an intolerable adverse event.

Once adequate control of chorea has been achieved, the dose of study drug should not be increased further.

Pharmacokinetic modeling and simulation of Phase 1 data were performed to estimate the overall systemic exposure (AUC) for various tetrabenazine and SD-809 ER regimens. Appendix 14 depicts the values for AUC₀₋₂₄ for extensive and intermediate metabolizers of CYP2D6.

Based on the data in Appendix 14, an initial SD-809 ER regimen has been identified which approximates the AUC₀₋₂₄ for total ($\alpha+\beta$)-HTBZ of the corresponding tetrabenazine total daily dose in CYP2D6 extensive and intermediate metabolizers (Table 1). Although the median AUCs for SD-809 ER are slightly lower than those for the corresponding tetrabenazine regimen, there is considerable overlap in the distributions of this parameter. Subjects with diminished CYP2D6 function (e.g., poor metabolizers or receiving potent CYP2D6 inhibitors) who undergo dose conversion according to Table 1 may have an initial AUC on SD-809 ER that is up to 30-40% below that of their tetrabenazine regimen (See Appendix 15). As with intermediate and extensive metabolizers, there is considerable overlap in the distribution of AUCs between SD-809 and tetrabenazine in poor metabolizers. Furthermore, subjects with inadequate control of chorea may undergo dose adjustment for the four weeks following initial dose conversion. Additional dose adjustments may be made after Week 4 if clinically indicated.

Table 1: Initial SD-809 Dose Regimen based on Incoming Tetrabenazine Regimen

If a Switch Subject's Incoming Total Daily TBZ Dose is:	Then, the Initial Total Daily SD-809 ER Dose Should Be:	Taken As:	
		Morning Dose	Evening Dose

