5.2.4 Dosing in Long Term Treatment

Initially during the long-term treatment period, a well-tolerated dose of SD-809 that provides adequate chorea control may not yet be established. Dose adjustments may continue during long term treatment as specified in Sections 5.2.2 and 5.2.3. Once a stable dose is achieved, SD-809 ER should be dosed at the same level throughout the remaining long term period. If necessary, however, the dose may be adjusted further during long term treatment (upward or downward) to optimize chorea control or minimize adverse events. In general, dose changes are limited to 6 mg per day (6 mg/day or 12 mg/day after a total daily dose of 48 mg is reached; See Section 5.2.5). However, such changes in dose should not occur more frequently than once per week.

Once subjects are on a stable dose of SD-809 ER, drug will be provided to study subjects in 30-count containers until the next specified visit. Each order will contain a sufficient supply of drug

¹ See Section 7 for evaluation of AEs regarding severity, relationship to study drug and definition of SAE.

until the next specified visit, plus overage to account for potential delays in study visits or evaluations or receipt of their supplies.

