- Assessment of medication accountability/compliance
- Evaluation of study drug dose level and adjustment, if necessary (through Week 4 for **Switch** subjects; through Week 8 for **Rollover** subjects)
- Re-order study medication (See Operations Manual for further details)
- Next clinic visit and telephone contact (Week 4 **Rollover** subjects only) will be scheduled/reconfirmed

Subjects switching from tetrabenazine (Switch subjects) should continue to receive their long term treatment dose after the Week 4 clinic visit, although further dose adjustments are permitted if clinically indicated.

Subjects from the SD-809-C-15 Study (Rollover subjects) should continue to receive their long term treatment dose after the Week 8 clinic visit, although further dose adjustments are permitted if clinically indicated.

Note (**Switch** subjects only): If a subject requires a dose change at Week 8, the Week 8 assessments should be conducted except for PK sampling which should be postponed until Week 15.

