7.2 Safety Endpoints

Safety and tolerability will be assessed throughout the study by monitoring the following:

- Incidence of adverse events (AEs), serious AEs (SAEs), severe AEs, drug-related AEs, and AEs leading to withdrawal during the following periods:
 - The entire post-baseline period
 - During the Titration Period (from Day 1 to the end of Week 8) in Rollover subjects
 - During the Dose-Adjustment Period (from Day 1 to the end of Week 4) in Switch subjects
 - During the Extended Dose-Adjustment Period (from Day 1 to the end of Week 8) in Switch subjects who undergo dose adjustment between Weeks 4 and 8 (if at least 10% of Switch subjects have had a dose adjustment between Week 4 and Week 8)
 - During the Stable-Dose Period (Week 8 to end of study)
- Observed values and changes from baseline in clinical laboratory parameters (hematology, chemistry, and urinalysis)
- Observed values and changes from baseline in vital signs
- Observed values in ECG parameters and abnormal findings

- Numbers of subjects with QTcF values > 450 msec, > 480 msec, > 500 msec
- Counts and percentages for Columbia Suicide Severity Rating Scale (C-SSRS)
- Observed values and changes from baseline in the following:
 - Unified Huntington Disease Rating Scale (UHDRS)
 - Unified Parkinson's Disease Rating Scale (UPDRS) (dysarthria)
 - Barnes Akathisia Rating Scale (BARS)
 - Hospital Anxiety and Depression Scale (HADS)
 - Epworth Sleepiness Scale (ESS)
 - Montreal Cognitive Assessment (MoCA[®])
 - Swallowing Disturbance Questionnaire (SDQ)
- Duration of time to achieve a stable dose of SD-809, defined as the number of days from Day 1 until the first day at which the subject was taking the dose level they were receiving at Week 8.

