9.5 Study Drug Exposure and Compliance

The Investigator or designated study staff is responsible for monitoring the subject's compliance with study drug during the trial. Compliance will be assessed by tablet count obtained from returned study drug containers and must be reviewed at every visit while the subject is still in the clinic to determine if the subject is taking study drug as directed.

Percent compliance in the interval between visits will be calculated as $100 \cdot (\text{number of tablets used} / \text{number of tablets expected to be used})$, where $\text{number of tablets used} = \text{number of tablets dispensed} - \text{number of tablets returned}$. A subject will be deemed compliant if the subject has taken 80% to 105% of the expected number of tablets of study drug; this definition of compliance supersedes the definition specified in the study protocol.

For Switch subjects, percent compliance will be summarized for the following time periods using descriptive statistics: from Day 1 to the Week 4 visit, from Day 1 to the Week 8 visit, and from Day 1 to the last dose of study drug. For Rollover subjects, percent compliance will be summarized for the following time periods using descriptive statistics: from the Day 1 to the Week 8 visit and from Day 1 to the last dose of study drug. Compliance will be summarized for these same time periods using counts and percentages.

The length of time (in days) that each subject is exposed to SD-809 will be summarized using descriptive statistics. For subjects who complete the study through Week 8, the duration of time in days from Day 1 until the day of first receiving the SD-809 dose received at Week 8 (i.e., the duration of time to achieve a stable dose of SD-809) will be summarized using descriptive

statistics. For Switch subjects who complete the study through Week 8, the number and percentage of subjects who achieve a stable dose by Week 4 (i.e., received the same dose of SD-809 at Week 4 that they received at Week 8) will be presented.

For each subject, the initial dose, titrations, and investigator-initiated dose changes that occur during the study will be listed.

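### Time to stable dose stops at the first day ever on the Week 8 dose, so a subject who leaves that dose and returns to it is scored too early, never too late

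*SAP*

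**What the plan says.** The protocol synopsis lists the endpoint as "Duration of time to achieve stable dosing of SD-809 ER". Neither the synopsis nor Protocol 8.4 defines stable, so the SAP alone fixes the meaning.

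- **Duration.** SAP 7.2 ends the count at "the first day at which the subject was taking the dose level they were receiving at Week 8". SAP 9.5 summarises it for subjects who complete through Week 8, counting "until the day of first receiving the SD-809 dose received at Week 8".
- **Stable by Week 4 (Switch only).** SAP 9.5 also gives the percentage who "received the same dose of SD-809 at Week 4 that they received at Week 8".
- **Listing.** SAP 9.5 says that, for each subject, "the initial dose, titrations, and investigator-initiated dose changes that occur during the study will be listed".
- **Protocol usage of stable.** Protocol 5.2.4 states: "Once a stable dose is achieved, SD-809 ER should be dosed at the same level throughout the remaining long term period". It then allows further adjustment if needed.
- **Dose movement.** SAP section 4 lets the dose go up or down weekly in 6 mg/day steps, with up to 12 mg/day once 48 mg is reached. This runs through Week 4 (Switch) or Week 8 (Rollover), and later if clinically indicated. On pace, Protocol 5.2.2 says "Changes in dose should not be made more often than once per week unless the subject is experiencing an intolerable adverse event".

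**The concern.** Being on a dose once is not the same as having settled on it. An increase followed by a reduction of the same size returns the subject to exactly the earlier dose, and the SAP rule then stops the clock at the first pass. For a Switch subject that earlier dose can be the conversion dose, so an increase that was later reversed is reported as settled on Day 1.

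The two stability measures in SAP 9.5 can also disagree about one subject, and the Week 4 measure compares only two visits and ignores what happened between them.

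Two readings are left open. The SAP does not say whether the Week 8 dose is the one the subject arrives on or the one set at that visit, although a change at Week 8 is foreseen for both cohorts (SAP Table 1 footnote 13; Table 2 dose evaluation at Week 8). Nor does it say how a suspension counts, although Protocol 5.2.5 allows one of up to a week and allows the full dose to be resumed.

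At stake is a protocol-listed endpoint that, for the Switch cohort, describes how soon subjects settle after conversion.

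**Working it through.** The plan gives no figure for this endpoint, so there is none to reproduce. The check applies the stated rule to permitted dose paths.

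**Inputs**
- Duration = (end date − start date) + 1 (SAP 8.7), so the value equals the study day number.
- The target day for Week n is 7n (SAP Table 3).
- Steps of 6 mg/day, at most weekly (SAP section 4).
- About 36 Switch and 80 Rollover subjects (Protocol section 3).
- Assumptions: a dose decided at Week n starts on Day 7n + 1; suspensions are ignored.

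**Formula.** Let A be the first day ever on the Week 8 dose (the SAP rule). Let B be the first day of the unbroken run on that dose that is still in force at Week 8. The start of that run is itself a day on the dose, so A ≤ B always. Gap = B − A.

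| Cohort | Doses (mg/day) | Start days | A | B | Gap |
|---|---|---|---|---|---|
| Switch | 24/30/24 | 1/8/15 | 1 | 15 | 14 |
| Switch | 24/30/24 | 1/15/22 | 1 | 22 | 21 |
| Switch | 24/30/24 | 1/22/29 | 1 | 29 | 28 |
| Switch | 24/30/24 | 1/22/36 | 1 | 36 | 35 |
| Switch | 24/30/24 | 1/36/50 | 1 | 50 | 49 |
| Rollover | 6/12/18/24/30/24 | 1/8/15/22/29/36 | 22 | 36 | 14 |
| Rollover, monotone | 6/12/18/24/30 | 1/8/15/22/29 | 29 | 29 | 0 |

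The first three Switch rows need only the scheduled contacts through Week 4. The last two need later unscheduled adjustments, which Protocol 6.3 permits. The Rollover rows use only the scheduled Week 1 to 5 contacts.

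**Against the Week 4 measure**
- Path 1/22/36: 30 mg at Week 4 and 24 mg at Week 8, so not stable by Week 4. The duration is still 1 day.
- Path 1/36/50: 24 mg at both visits, so stable by Week 4, despite 30 mg on Days 36 to 49.
- Path 1/22/29: not stable if the Week 4 dose is the one coming in (30 mg), stable if it is the one set there (24 mg).

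**All paths** with weekly steps of −6, 0 or +6 mg, a 6 mg floor and a 72 mg cap:

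| Start dose | Changes at Weeks | Paths | Gaps found (days) |
|---|---|---|---|
| Switch 24 mg | 1–4 | 80 | 0, 14, 21, 28 |
| Switch 24 mg | 1–7 | 2038 | 0, or 14 to 49 in steps of 7 |
| Rollover 6 mg | 1–5 | 96 | 0, 14, 21, 28, 35 |

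No gap is negative. In the 2038 Switch paths A is earlier than B in 1296, equal in 742 and later in none. These counts show what is possible and in which direction, not how often it happens.

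**Effect on the mean** = share affected × gap. The shares are assumptions.

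| Share | Gap 14 | Gap 28 | Gap 35 | Gap 49 |
|---|---|---|---|---|
| 5% | 0.7 | 1.4 | 1.75 | 2.45 |
| 10% | 1.4 | 2.8 | 3.5 | 4.9 |
| 20% | 2.8 | 5.6 | 7.0 | 9.8 |

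**The case against.** The protocol leaves the endpoint undefined, the SAP supplies one explicit rule and states it consistently, and time to achieve a dose can be read as time to first reach it. Protocol 5.2.4 is a conduct rule that itself allows later changes. The alternative has an oddity too: five weeks on 24 mg, one week on 30 mg and then 24 mg again scores Day 43, although the final dose was in use from Day 1. The protocol also leans towards one-way titration, with a low start for Rollover subjects, conversion to comparable exposure for Switch subjects and no increase once chorea is controlled. Dose by visit (SAP 9.8), the listed dose changes (9.5) and adverse events leading to dose reduction or suspension (9.9.1) already show much of this.

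Several of these points stand. The frequency is unknown, the measure is descriptive (SAP 8.1), and the one-way error applies to subjects who leave and resume, measured against the unbroken run. A subject long settled who changes just before Week 8 scores late under both rules. The reading of the Week 8 dose as the incoming one is the more natural, but it is not stated.

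They do not remove the problem. First reaching a dose is a usable measure, but it is not stability, and the SAP's own Week 4 measure can call the same subject unstable. In the Day 43 example the subject's last change was on Day 43, which is what a time to stable dose should show. The other displays give context but do not correct the reported duration or percentage.

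**Conclusion.** The concern holds. Applied as written, the rule scores a subject who leaves and resumes the Week 8 dose at the first pass, and for such subjects the error only shortens the time. The individual gaps are 14 to 49 days for Switch subjects who return to the conversion dose, 14 days in the Rollover example, and zero for monotone titration. The exact days rest on the assumed start on Day 7n + 1; the direction does not. The effect on a cohort mean depends on a share that the documents do not give. Anchoring at Week 8 is not in dispute, and no test or sample size is affected. The change should be made because the endpoint is protocol-listed and the correction is cheap.

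**What to change.** 1. In SAP 7.2 and 9.5, count to the first day of the unbroken run at the Week 8 dose that lasts to Week 8.
2. State whether the Week 8 dose is the one coming into the visit or the one set at it, and use the same reading at Week 4.
3. State how a suspension followed by a return to the same dose counts.
4. For Switch subjects stable by Week 4, require no dose change from Week 4 through Week 8.

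Optionally, report beside the summary how many subjects stopped before Week 8 and how many changed dose at or after Week 8.

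The cost is SAP wording and minor programming on dose records that SAP 9.5 already lists. Once the readings in items 2 and 3 are fixed, each subject's time stays the same or lengthens, and the Week 4 percentage stays the same or falls. The choice of reading can itself move that percentage either way, so it should be made before the results are seen.

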7.3 Rating Scales

7.3.1 Hospital Anxiety and Depression Scale (HADS)

The HADS is a self-administered instrument reliable for detecting states of depression and anxiety in an outpatient medical setting. The scale consists of 14 items (7 each for anxiety and depression). Each item is rated on a four-point scale ranging from 0 (not at all) to 3 (very often). Responses are based on the relative frequency of symptoms over the preceding week.

7.3.2 Columbia Suicide Severity Rating Scale (C-SSRS)

The C-SSRS is an FDA endorsed questionnaire to screen for suicidality in trials of central nervous system active compounds. The C-SSRS is an interview by trained study personnel that should be done at Screening, Baseline (Day 0), and during the study as outlined in the Schedule of Events. The form provided at Screening collects the history of suicide using a C-SSRS form version termed "Baseline", and subsequent visits use a C-SSRS form version termed "Since the Last Visit."

7.3.3 Unified Huntington Disease Rating Scale (UHDRS)

The UHDRS is a research tool which has been developed by the HSG to provide a uniform assessment of the clinical features and course of HD. The components of the UHDRS are:

- Motor Assessment, which includes the total maximal chorea (TMC) score and the parkinsonism subscale score (sum of finger taps, pronate/supinate - hands, rigidity - arms, bradykinesia - body, gait, tandem walking, and retropulsion pull test scores)
- Cognitive Assessment
- Behavioral Assessment
- Independence Scale

- Functional Assessment
- Total Functional Capacity (TFC)
- Clinical Summary

7.3.4 Montreal Cognitive Assessment (MoCA[®])

The MoCA[®] is a validated rapid screening instrument for assessing mild cognitive dysfunction. It assesses different cognitive domains: attention and concentration, executive functions, memory, language, visuoconstructional skills, conceptual thinking, calculations, and orientation. The total possible score is 30 points; a score of 26 or above is considered normal. There are 3 versions in the English language. Given the relatively frequent use of this instrument, the versions will be rotated at each visit.

7.3.5 Unified Parkinson Disease Rating Scale (UPDRS)

The UPDRS is a comprehensive instrument used to assess the signs and symptoms of Parkinson's disease. The UPDRS is comprised of various patient and clinician based assessments of motor, cognitive, and behavioral symptoms. UPDRS questions pertaining to speech/dysarthria will be utilized to screen and monitor study subjects for parkinsonism.

7.3.6 Barnes Akathisia Rating Scale (BARS)

The BARS is a widely used rating scale for evaluation of drug induced akathisia. This scale includes an objective assessment, subjective measures, including self-awareness and distress, and a global clinical assessment.

7.3.7 Epworth Sleepiness Scale (ESS)

The ESS is a self-administered questionnaire, composed of eight questions, that provides a measure of a subject's general level of daytime sleepiness. The ESS asks respondents to rate, on a 4-point Likert scale (0 – 3), their usual chances of dozing off or falling asleep in different situations or activities that most people engage in as part of their daily lives. The total ESS score is the sum of 8 item-scores and can range between 0 and 24, with higher scores indicating a higher level of daytime sleepiness.

7.3.8 Swallowing Disturbance Questionnaire (SDQ)

The SDQ is a self-administered questionnaire comprising 15 questions that assess the frequency of swallowing disturbance. Scores range from 0.5 (normal) to 44.5 (severe impairment).

8 Statistical Methods

8.1 Hypothesis Testing

Because this is an open-label, single-arm trial, no formal statistical analyses will be conducted.

8.2 Sample Size

This is an open-label, single-arm safety study, and the sample size is not based on statistical considerations.

8.3 Subject Withdrawal

Subjects may withdraw from the study at any time. Subjects may be withdrawn from study treatment or the study at the request of the Investigator or Sponsor.

Notification of early subject discontinuation from the study and the reason for discontinuation will be made to the Clinical Monitor and will be clearly documented on the appropriate eCRF page. If a subject is discontinued from the study early, all early termination evaluations should be performed at the time of discontinuation, if possible.

8.4 Final Analyses and Reporting

For Rollover subjects from the First-HD study, the subject's prior treatment assignment (SD-809 or placebo) will remain blinded until that study's final database has been locked and unblinded.

The final databases for this study may not be locked until this SAP has been approved. The analyses outlined in this SAP will be carried out after:

- The SAP has been approved;
- The corresponding study database has been authorized by the sponsor clinical team as complete and finalized.

Further exploratory analyses not necessarily identified in this SAP may be performed to support the clinical development program. Any post-hoc or unplanned analyses performed and not identified in this SAP will be clearly identified in the CSR.

8.5 Handling of Missing Data

8.5.1 Missing Data for Individual Items of an Instrument

For the Total Motor Score and the TMC Score of the UHDRS, missing data items will be imputed, provided that at least 80% of the items for the corresponding score are nonmissing. In such cases, the value(s) of the missing item(s) will be imputed by carrying forward the most recent nonmissing value of the corresponding item. However, if more than 20% of the items for the score are missing, the score will be treated as missing.

For all other missing data items, the missing data items will remain missing and will not be imputed, and only observed data will be summarized.

